5.4.1 Handling of Withdrawals

A subject may choose to discontinue participation in the study at any time. An Early Termination visit will occur when a subject withdraws consent, i.e. withdrawing his or her participation in future study procedures

5.5 Termination of Study

This study may be prematurely terminated if, in the opinion of the investigator, there is sufficient reasonable cause.

Circumstances that may warrant termination include, but are not limited to:

- Determination of unexpected, significant, or unacceptable risk to subjects.
- Unsatisfactory enrollment.
- Insufficient adherence to protocol requirements.
- Data that are not sufficiently complete and/or evaluable.

If the study is prematurely terminated or suspended, the investigators will promptly inform the institution and regulatory authorities of the termination or suspension and the reason(s) for the termination or suspension. The IRB/IEC will also be informed promptly and provided the reason(s) for the termination or suspension by the investigator, as specified by applicable regulatory requirement(s).

Version:4.4

A Crossover, Randomized Block Sequence, Double-Blind, Placebo-Controlled Trial for Nicotinamide Riboside in Subjective Cognitive Decline and Mild Cognitive Impairment in Aging

6. **STUDY PROCEURES**

6.1 **Schedule of Assessments**

	Days -28 to -1 Screening Visit ¹	Day 0 Lead-in	Day 28 ± 4 days Baseline	Day 56 ² ± 4 days Block 1 Midway	Day 84 ± 4 days Crossover (PBO/NR)	Day 112 ² ± 4 days Block 2 Midway	Day 140 ± 4 days End of Study	Day 154 ± 4 days Follow Up ¹	Early Termination
Informed Consent ^{1,3}	X								
Informed Consent Worksheet ¹	X		X		X		X		
Demographics ¹	X								
Medical History ^{1,4}	X	X	X	X	X	X	X	X	X
Height & Weight		X							
Vital Signs		X	X		X		X		X
Inclusion/ Exclusion Review ¹	X	X							
Safety Labs ⁵		X					X	X^6	X
Concomitant Medications & Supplements ¹	X	X	X	X	X	X	X	X	X
Physical & Neurological Examination		X	X		X		X		
Cognitive Screening Measures ^{1,7}	X								
Test of Premorbid Functioning		X							
Randomization		X							
Dispense Supplement/Placebo		X	X		X				
Accountability and Compliance			X	X	X	X	X		X

A Crossover, Randomized Block Sequence, Double-Blind, Placebo-Controlled Trial for Nicotinamide Riboside in Subjective Cognitive Decline and Mild Cognitive Impairment in Aging Version: 4.4
Version date: May 26, 2022

	Days	Day 0	Day 28	Day 56 ²	Day 84	Day 112 ²	Day 140	Day 154	Early
	-28 to -1		± 4 days	± 4 days	± 4 days	± 4 days	± 4 days	± 4 days	Termination
	Screening Visit ¹	Lead-in	Baseline	Block 1 Midway	Crossover (PBO/NR)	Block 2 Midway	End of Study	Follow Up ¹	
Virtual Cognitive Assessment ^{1,8}			X		X		X		X
Virtual Neuropsychiatric Surveys ^{1,9}			X		X		X		X
Virtual Functional Survey ^{1,10}			X		X		X		X
Blood Collection for Biomarker Analysis		X	X		X		X		X
Technology Training/Check-in		X	X	X	X	X	X		
Daily Cognitive Assessment ¹¹									
Daily Mood and Sleep Assessment									
Daily Activity Assessment ¹²							-		
Lumbar Puncture ¹³			optional		optional		optional		
fMRI Scan			optional		optional		optional		
Adverse Events ^{1,14}	X	X	X	X	X	X	X	X	X

¹These visits and procedures will take place virtually via Zoom videoconference and will take place up to 4 business days prior to the office visit date. If the subject resides out of state, their screening visit will take place in person at MGH CNY campus.

A Crossover, Randomized Block Sequence, Double-Blind, Placebo-Controlled Trial for Nicotinamide Riboside in Subjective Cognitive Decline and Mild Cognitive Impairment in Aging Version: 4.4

²Block Midway visits will be conducted over the telephone. The participant will not be required to come in MGH for these visits.

³No study procedures apart from the telephone pre-screening visit will be performed prior to the signing of the informed consent form (ICF). All subjects will sign an ICF prior to undergoing any study tests or procedures.

⁴After initial assessment of medical history during the screening period, updated medical history will be collected in subsequent visits.

⁵ Safety labs include Hematology (CBC with differential), Complete Chemistry Panel, Liver Function Tests, B12 and TSH.

⁶Safety labs will only be drawn if any labs from the End of Study (Day 140) Visit were abnormal and clinically significant.

⁷Including T-MoCA (or MoCA), BDI and IADL Scale.

⁸Including RBANS, CPT, BVMT, DKEFS Verbal Fluency Subtest, and Trail Making Test.

⁹Including BDI/BAI.

¹⁰Including MFQ and BRIEF-A.

¹¹Lumosity Brain Games (Lumos, Labs, Inc.)

¹²Fitbit Charge 3 Wearable Device

¹³CBC, PT/INR point of care @ Days 28, 84 and 140 if undergoing optional LP

¹⁴ All adverse events that occur AFTER signing consent form until the end of the follow up visit will be included.
A Crossover, Randomized Block Sequence, Double-Blind, Placebo-Controlled Trial for Nicotinamide Riboside in Subjective Cognitive Decline and Mild Cognitive Impairment in Aging Version:4.4 Version date: May 26, 2022

6.1.1 Screening Visit (Day -28)

Subjects located outside the state of Massachusetts will complete their screening visit in person. Subjects located in Massachusetts will complete a virtual screening visit via Zoom videoconference. The screening procedures will determine the subject's eligibility for the study and will take approximately 2 hours.

The following procedures will take place at the Screening visit:

- Obtain written informed consent from the subject after assessment of capacity to consent via the Informed Consent Worksheet.
- Obtain demographics and medical history
- Administer T-MoCA (or MoCA), BDI and IADL Scale
- Review and document concomitant medications, supplements, and therapies
- Assess inclusion and exclusion criteria to determine subject eligibility
- Assess and document adverse events (AEs) after subject signs informed consent form (ICF)

6.1.1.1 Screen Failures

Any subject who signs consent will be considered enrolled in the study. If a subject fails screening, at a minimum, the following information should be captured and entered into the Electronic Data System (EDC).

- Inclusion/Exclusion Criteria
- Demographics
- Reason for screen failures

6.1.2 Lead-In Visit (Day 0)

This visit will take place within 28 days of the Screening Visit. The following procedures will be performed and will take approximately 1.5 hours.

The following procedures will take place at the in-person office visit:

- Measure Vital Signs
- Physical and Neurological examination
- Blood draw for safety labs and biomarker analysis
- Dispense PBO
- Explain and practice how to use technological devices and software that will be used during study-computer, daily Lumosity brain games, Fitbit device, Fitbit software.
- Administer TOPF
- Assess inclusion and exclusion criteria to determine subject eligibility

6.1.2.1 Technology Check-In Phone Calls- Days 1, 7, and 21

At Days 1, 7, and 21 (± 1 day) during the initial Lead-in Period, a study coordinator will call the subject to ensure they understand how to use all technology and discuss compliance if necessary. The subjects will also be provided with the study coordinator's phone number and email and encouraged to contact the study coordinator with questions or concerns at any time.

A Crossover, Randomized Block Sequence, Double-Blind, Placebo-Controlled Trial for Nicotinamide Riboside in Subjective Cognitive Decline and Mild Cognitive Impairment in Aging

Version:4.4

6.1.3 Baseline Visit (Day 28), Crossover Visit (Day 84), and End of Study Visit (Day 140)

These visits will occur 28 days (\pm 4 days) after the previous visit. These visits will occur in two parts: the first portion will occur virtually via Zoom videoconference no more than 4 days prior to the second portion, which will be an office visit. The following procedures will be performed and will take approximately 2.5-6 hours depending on participation in LP and MRI sub-studies. If the subject has elected to participate in the LP and/or MRI sub-study, the visit may occur over multiple days as long as all tasks are completed during the study visit window.

The following measures will be performed virtually via Zoom videoconferencing no more than 4 days prior to the office visit:

- Assessment of capacity to consent through administration of the Informed Consent Worksheet
- Administer cognitive assessments
- Administer functional and mood assessments
- Assess technology compliance
- Assess and document AEs and changes to medical history
- Review and document concomitant medications, supplements, and therapies

The following procedures will occur in person:

- Measure Vital Signs
- Perform physical and neurological examinations
- Blood draw for biomarker analysis
 - o End of Study (Day 140) only- additional tubes for safety labs
 - o If undergoing LP, then an additional fingerstick for point of care, same day PT/INR will also be performed
- Assess study supplement compliance
- Dispense study supplement or PBO (except at End of Study Visit)
- Perform optional MRI scan
- Perform optional fasting LP

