3.2 Study Objectives

A Crossover, Randomized Block Sequence, Double-Blind, Placebo-Controlled Trial for Nicotinamide Riboside in Subjective Cognitive Decline and Mild Cognitive Impairment in Aging

Version:4.4

The primary objective of the study will be:

1. To measure the effect of NR vs PBO on RBANS.

The secondary clinical objectives of the study will be:

- 1. To measure the effect of NR vs PBO on other, standard assessments of cognition, functional activities, and neuropsychiatric symptoms.
- 2. To measure the effect of NR vs PBO on daily assessments of cognition, functional activities, and neuropsychiatric symptoms.
- 3. To monitor the safety and tolerability of NR in volunteers with SCD or MCI.

The exploratory biomarker objectives of the study will be:

- 1. To measure the effect of NR on plasma biomarkers of metabolic target engagement and central nervous system (CNS) neural and glial integrity measurable in blood.
- 2. To measure the effects of NR on cerebral neurophysiology (in an optional sub-study) using resting state functional magnetic resonance imaging (rs-fMRI). Connectivity will be measured with rsBOLD and regional cerebral blood flow will be measured with pseudo-continuous arterial spin labeling (pCASL).
- 3. To measure the effect of NR on cerebrospinal fluid (CSF) biomarkers (in an optional sub-study) of metabolic target engagement and emerging biomarkers of relevance to AD/ADRD.

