 - Optional MRI will be conducted at three time points: Baseline (Day 28), Crossover (Day 84), and End of Study (Day 140. Each MRI scan session will include functional MRI with resting state BOLD (rs-fMRI) and pseudo-continuous arterial spin labeling (pCASL) sequences. rs-fMRI measures spontaneous yet synchronized fluctuations in the BOLD signal to determine the strength of functional connectivity within various intrinsic brain networks (i.e., default mode network). pCASL quantifies regional cerebral blood flow using magnetically labeled blood water content and will serve as a marker of resting state cerebral perfusion that has also been shown to correlate with regional brain metabolism and levels of neuronal activity.
- Cerebrospinal Fluid Biomarkers (optional sub-study): All subjects will have the opportunity to participate in a lumbar puncture (LP) sub-study in which they can receive 1-3 optional LPs at Baseline (Day 28), Crossover (Day 84), and End of Study (Day 140). A panel of CSF biomarkers will be measured to determine the effects of NR on pathophysiological targets relevant to aging and neurodegeneration, including 1) neuronal degeneration markers neurofilament light chain (NfL) and neurogranin, 2) classic AD biomarkers including amyloid-β_{42/40}, total tau and phospho-tau, 3) markers of mitochondrial function and redox dysregulation such as 8-hydroxy-2'-deoxyguanosine (8-OHdG) and pyruvate/lactate, and 4) selected other biomarkers of inflammation and immune response and vascular injury of relevance to the aging brain and cognition.

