4.2 Recruitment

Approximately 60 subjects will be screened, and after screening, approximately 40 subjects are expected to complete the study. All subjects will be given the option to participate in the optional repeat LP sub-study and the optional MRI sub-study until 12 subjects have completed each sub-study. Subjects will be given the choice to complete either the repeat LP sub-study, the MRI sub-study, or both.

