5.3 Randomization

A Crossover, Randomized Block Sequence, Double-Blind, Placebo-Controlled Trial for Nicotinamide Riboside in Subjective Cognitive Decline and Mild Cognitive Impairment in Aging

Version:4.4

Subjects will be randomized into one of two counter-balanced block sequences (see Figure 4 below). Randomization will be done by MGH Clinical Trials Pharmacy.

[figure not shown]

Figure 4. Study Schema

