6.1.6 Early Termination Visit

If the subject withdraws from the study after the Baseline visit and before completion of all study visits, they will be invited to participate in an Early Termination Visit within 7 days of stopping treatment.

The following procedures will be performed virtually via Zoom videoconferencing no more than 4 days before the in-person office visit:

- Administer cognitive assessments
- Administer functional and mood assessments
- Assess technology and study supplement compliance.
- Review and document concomitant medications, supplements, and therapies
- Assess and document AEs and changes to medical history

The following procedures will be performed at the in-person office visit:

- Measure Vital Signs
- Blood draw for safety labs and biomarker analysis
- Assess study supplement compliance

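### No full safety panel is scheduled at Day 84, so NR-first completers have none on NR and chemistry, liver tests, B12 and TSH have no within-subject NR-placebo contrast

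*Combined protocol and SAP*

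**What the plan says.** The Safety Labs row of the section 6.1 schedule is marked at Day 0, Day 140, Day 154 and Early Termination, and is blank at Days 28, 56, 84 and 112. Footnote 5 defines the panel: "Safety labs include Hematology (CBC with differential), Complete Chemistry Panel, Liver Function Tests, B12 and TSH". Footnote 6 makes the Day 154 draw conditional on a clinically significant abnormality at Day 140.

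The visit text agrees. The Day 0 visit (section 6.1.2) lists "Blood draw for safety labs and biomarker analysis". For the three later office visits, section 6.1.3 says "End of Study (Day 140) only- additional tubes for safety labs". Biomarker blood is drawn at Day 84 in any case (section 6.1 schedule, sections 6.1.3 and 7.1.2.4).

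On numbers, section 4.2 says "approximately 40 subjects are expected to complete the study", and section 5.3 says "Subjects will be randomized into one of two counter-balanced block sequences" without giving a ratio.

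The third secondary objective (section 3.2) is "To monitor the safety and tolerability of NR in volunteers with SCD or MCI". Section 3.2.1 measures it by adverse event reporting at every visit, and section 11.3.1 counts clinically significant laboratory values as adverse events.

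**The concern.** A symptom-free change in liver or chemistry values is found only by drawing blood. Block 1 ends at Day 84 and block 2 at Day 140, so a panel at Day 140 alone sees each subject under only one of the two treatments. For the NR-first half that treatment is placebo, about eight weeks after the last NR dose.

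Two things are at stake for the safety objective: how many subjects could show a laboratory abnormality while on NR, and whether a laboratory difference can be attributed to NR with the within-subject comparison that the crossover was chosen to provide. Section 9.1 itself says that NR's pharmacodynamic effects may outlast its short half-life and that carryover cannot be ruled out. That bears on the one randomized laboratory comparison that remains, between sequences at Day 140.

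**Working it through.** The plan gives no figure for this point, so there is none to reproduce.

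**1. Treatment state at each possible panel**

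| Day | Full panel | NR-first | Placebo-first |
|---|---|---|---|
| 0 | yes | untreated | untreated |
| 28 | no | end of placebo lead-in | end of placebo lead-in |
| 84 | no | end of NR | end of placebo |
| 140 | yes | end of placebo | end of NR |
| 154 | conditional | off | off |

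With 40 completers and 1:1 allocation (assumed), 40 × 0.5 = 20 have no scheduled on-NR panel, and 0 of 40 have both an NR and a placebo panel. For NR-first completers the gap from the end of NR to the Day 140 panel is 140 − 84 = 56 days, or 48 to 64 with the ±4-day windows.

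**2. The blood-count exception.** Footnote 13 gives lumbar puncture participants a point-of-care CBC at Days 28, 84 and 140. Section 4.2 offers that sub-study until 12 subjects complete it. If half of those 12 are NR-first, on-NR CBCs number about 20 + 6 = 26. The count is higher if other NR-first subjects have a single puncture at Day 84, since section 3.2.1 allows one to three.

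**3. Detection, if an NR change reverses before Day 140.** Only on-NR panels can then show it: n = 20 now, n = 40 with Day 84 added.

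- Zero-event one-sided 95% upper bound, 1 − 0.05^(1/n): 13.9% at n = 20 and 7.2% at n = 40.
- Chance of at least one event, 1 − (1 − p)^n. The documents give no rate, so a range is shown:

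| Assumed rate p | n = 20 | n = 40 |
|---|---|---|
| 1% | 18.2% | 33.1% |
| 5% | 64.2% | 87.1% |
| 10% | 87.8% | 98.5% |

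If the change reaches only a fraction f of NR-first subjects, n = 20 + 20f. For f = 0.25, 0.5 and 0.75, n = 25, 30 and 35, with bounds of 11.3%, 9.5% and 8.2%. If completers split 16:24 either way, the present n is 16 to 24, with a bound of 17.1% to 11.7%.

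**4. Detection, if the change persists to Day 140.** The Day 140 panels of both sequences can already show it against Day 0. With full persistence the effective count is already about 40, so step 3 no longer measures the gain.

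**5. The treatment contrast.** Let d be the NR effect and L the share of it still present in NR-first subjects at Day 140.

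- Day 140 between sequences (available now): d − Ld = (1 − L)d.
- Within subject, Days 84 and 140: [(d − Ld) + d]/2 = (1 − L/2)d.
- Day 84 between sequences: d, because the placebo group has not yet had NR.

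At L = 0 all three are unbiased. At L = 0.5 they recover 50%, 75% and 100% of d.

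**6. Precision without carryover.** In SD units, with an assumed within-subject correlation r, the Day 140 contrast adjusted for Day 0 has SE √[(2/20)(1 − r²)], and the within-subject contrast has SE √[2(1 − r)/40]. At r = 0.5 these are 0.274 and 0.158. At r = 0.3 they are 0.302 and 0.187, and at r = 0.8 they are 0.190 and 0.100. The Day 84 between-sequence contrast has the same SE as the present Day 140 one, so under carryover its benefit is less bias, not a smaller SE.

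**The case against.** The passages agree with one another, so this is a design choice and not a contradiction. Safety is assessed by adverse event reporting, which covers both blocks in both sequences; vital signs and examinations are also scheduled at Days 84 and 140. No laboratory endpoint is defined, and section 9.1 calls every outcome exploratory. Step 6 therefore quantifies an analysis that the plan does not contain.

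Prior concern is modest. The hematology decreases in section 2.1.4 were slight and came from eight uncontrolled subjects escalated to 1000 mg twice daily, against 500 mg twice daily here (section 8.3). The placebo-controlled crossover in section 2.1.5, at 600 mg twice daily, saw no significant laboratory change. Other routes to a laboratory value also exist: investigators may order tests for an adverse event (section 7.1.1.2), and for early withdrawals "they will be invited to participate in an Early Termination Visit within 7 days of stopping treatment", with safety labs drawn. The documents do not say how many subjects are still short of Day 84.

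All of this stands, and it limits the weight of the point. It does not close the gap. Early Termination draws do not apply to completers, event-driven tests need an event to prompt them, and the sub-study's point-of-care tests include no chemistry or liver tests.

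Three stronger readings are tempting and not supported:

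- A reader might infer that no safety laboratory test has a within-subject contrast. Footnote 13 provides one for CBC in lumbar puncture participants.
- A reader might infer that the Day 140 comparison is invalid because its placebo group has already taken NR. If the change has reversed by then, the comparison is unbiased and only precision and panel count suffer.
- A reader might infer that section 7.1.1.2 drops the Day 140 panel. It conditions the follow-up draw on Day 140 results, so it presupposes that panel and merely fails to list it.

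**Conclusion.** The point holds as a cheap improvement, not a fatal flaw. By schedule, about 20 of 40 completers have no full panel on NR, and none has both an NR and a placebo panel. The count of 20 assumes 1:1 allocation.

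The size of the consequence depends on the laboratory change. If it reverses before Day 140, the cost is half the on-NR panels: a zero-event bound of 13.9% where 7.2% is available, and a loss of 11 to 23 percentage points in the chance of seeing any case at assumed rates of 1% to 10% (about 15, 23 and 11 points at 1%, 5% and 10%). If it persists, detection against Day 0 is largely in place already, and the cost is a Day 140 between-sequence contrast shrunk by the persisting share. The detection figures should not be quoted without the reversal condition. The primary RBANS analysis is not affected.

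**What to change.** Add the safety-lab tubes to the biomarker draw already scheduled at Day 84, so that each completer reached has one panel at the end of NR and one at the end of placebo. Summarise laboratory values by the treatment just completed, with treatment, period and sequence terms and Day 0 as reference. Also report the Day 84 between-sequence contrast, and rely on it if carryover is suspected. State how many subjects had passed Day 84 before the change.

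The cost is one more panel per subject and about 13 mL of blood (assuming the Lead-In volume), on top of the research total of about 120 ml in section 7.1.2.4. There is no new visit or needle-stick. An amendment and a consent update are needed, and subjects already past Day 84 gain nothing.

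Separately, and as an editorial matter, reconcile section 7.1.1.2 with the section 6.1 schedule and section 6.1.3. It does not list the Day 140 draw, and its 22 ml total leaves 22 − 13 = 9 mL after Lead-In without saying which later draw or draws that covers.

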6.1.4 Block Midway Telephone Visits (Days 56 and 112)

These visits will be conducted over the phone 28 days (\pm 4 days) after the previous visit. The following procedures will be performed and will take approximately 30 minutes.

- Assess technology and study supplement compliance
- Review and document concomitant medications, supplements, and therapies
- Assess and document AEs and changes to medical history

6.1.5 Follow Up Visit (Day 154)

This visit will take place after 14 days (\pm 4 days) following the Day 140 visit. The following procedures will be performed. All procedures will be performed virtually via Zoom videoconferencing or by telephone.

- Review and document concomitant medications, supplements, and therapies
- Assess and document adverse events (AEs) and changes to medical history
- Debriefing with Investigator on subject's data during trial and experience in the study

A Crossover, Randomized Block Sequence, Double-Blind, Placebo-Controlled Trial for Nicotinamide Riboside in Subjective Cognitive Decline and Mild Cognitive Impairment in Aging

If any labs from Day 140 were abnormal and clinically significant, the subject will also be asked to come in for an office visit blood draw for safety labs within the Follow up visit window.

